
A variety of potential mechanisms have been invoked to explain the beneficial effects of empagliflozin on CV mortality and hospitalization for heart failure and these have been the subject of recent reviews (8-10). Of the potential mechanisms responsible for the improved CV benefit, hemodynamic factors, including the simultaneous reduction in preload (8) (secondary to mild intravascular volume depletion) and afterload (secondary to reduced blood pressure [8] and improved aortic distensibility [16] most commonly have been cited. However, the ketone hypothesis provides an alternative and attractive explanation (17,18).

**HYPOTHESIS:** Elevated plasma ketone levels following initiation of SGLT2 inhibitor therapy in high risk type 2 diabetic individuals improves LV diastolic and systolic function and provides an explanation, in part, for the cardiovascular benefit observed in the EMPA REG OUTCOME and CANVAS trials.

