**Study Protocol:** Up to 100 Study participants will be asked to fast prior to consenting to the study and the day of the screening visit (day -30 to -7) participants will first sign consent form and eligibility criteria (A1c, eGFR, BP etc) will be confirmed and subjects will undergo a medical history and physical exam to exclude major organ system diseases other than diabetes and cardiac disease. Routine blood chemistries, CBC, urinalysis, lipid profile, TSH/T4, NT-proBNP, and EKG will be obtained. Blood pressure will be measured after reclining for 5 minutes in a quiet room and the mean of three measurements will be recorded. Subjects also will have a DEXA to measure total body fat content. If patient has not had an ECHO within 3-6 months of the screening visit, we will refer patient to the cardiac ECHO to confirm that the EF is < 50% (76).

Within 1-4 weeks after the screening visit, subjects will return to the Research Institute (RI) at 0700 h for a cardiac MRI (19,77) to confirm that the EF is < 50% and to obtain quantitative measures of baseline cardiac functional parameters: chamber volumes and pressures, wall thickness, LV diastolic function (E/A ratio, peak LV filling rate, diastolic volume) and LV systolic function (cardiac output, stroke volume, systolic volume, peak LV ejection rate). Strain and tagging also will be measured. To reduce the likelihood of hypoglycemia during the study procedures, subjects will be asked to withhold their antidiabetic therapy on the day of the studies until they have received a meal at the end of the study days.

Cardiac MRI will be performed by [name]. (Professor, Department of Radiology, UTHSCSA) on 3.0T MRI System (TIM, Trio, Siemens Medical Solution, Malvern, PA) with six channel anterior phased-array torso coil and corresponding coil elements (12 channels total) (19,77). Before cardiac MRI, catheters will be inserted into both antecubital veins for all blood withdrawal and  $\beta$ -OH-B infusion, respectively. Three blood samples will be drawn at 10-15 minute intervals for measurement of NT-proBNP, -OH-butyrate, acetoacetate,

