### **Data Analysis**

MRI data will be analyzed blindly by one of the investigators ([name]) using a commercial post-processing package (CMR42, Circle Cardiovascular Imaging Inc., Calgary AB). CMR42 function module performs global and regional LV function analyses on slices acquired in short axis orientation. LV volumes and myocardial mass are calculated with trabeculae and papillary muscles included. The CMR42 flow module computes velocity, flow, regurgitant volumes, and cardiac output. Ejection fraction (EF) is computed using end diastolic volumes (EDV) and end systolic volumes (ESV). For determining differences before and after  $\beta$ -OH-B, dimensional parameters are normalized to body surface area (BSA), using Mosteller formula (81). Ejection and filling functions are assessed from the respective maximal and average downslope and upslope of volume time curves to determine peak LV ejection (PLVER) and filling (PLVFR) rates.

PET sinograms are corrected for tissue attenuation and reconstructed through standard reconstruction algorithms. Image manipulation and data handling are performed using Carimas 2 (Turku PET Centre, Turku, Finland) software (82). The input function for FDG is derived from continuous monitoring of arterialized blood radioactivity. Whole blood is converted into plasma input using a limited number of discrete plasma samples. Delay correction is performed. Arterial input for O-water is obtained from the left atrium time activity curve. All of the PET data will be analyzed by [name] who has been a long term collaborator with Diabetes Division faculty members (19,20,22,78,79).

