## Expected Results

Studies in rodent models of heart failure and in humans with heart failure (31,33,38,39,71,83-86) have demonstrated that ketone utilization by the failing heart is increased. However, no study in humans has examined the effect of exogenous infusion of ketones on myocardial function and myocardial glucose utilization in nondiabetic or type 2 diabetic patients with heart failure. We expect that ketone infusion to elevate the plasma ketone concentration by physiologic (+0.5 mmol/L) and pharmacologic (+2.0 and +5.0 mmol/L) levels will cause a dose-response increase in parameters of LV diastolic/systolic function and a dose-response decrease in glucose utilization ( $^{18}\text{F}$ -2-DOG). Although not measured in the present study, we also would expect increased myocardial  $\beta$ -OH-B uptake to complete with fat oxidation since they share a common intermediate, i.e. acetyl CoA, that feeds into the Krebs Cycle. Because of its favorable P/O ratio and other potential metabolic benefits (17,18), we also expect that multiple parameters of LV diastolic (E/A ratio, diastolic volume, peak LV filling rate), as well as systolic (cardiac index, EF, peak LV ejection rate), function will increase. The present results will allow us to define the plasma  $\beta$ -OH-B concentration at which the substrate's beneficial effects on CV function are observed. We anticipate that elevation of the plasma  $\beta$ -OH-B level to 2.0-5.0 mmol/L, i.e. levels that are observed in 5-10% of individuals treated with SGLT2 inhibitors, will elicit a significant improvement in multiple parameters of LV systolic and diastolic function. If so, the "ketone hypothesis" (17,18) would be supported and explain, at least in part, the beneficial effect of empagliflozin and canagliflozin on hospitalization for heart failure and CV mortality in the EMPA REG OUTCOME and CANVAS studies. If beneficial effects on myocardial function are observed with the low dose  $\beta$ -OH-B infusion (increment in plasma  $\beta$ -OH-B =  $\sim$ 0.5 mmol/L), this will allow the results to be generalized to the great majority of diabetic patients treated with SGLT2 inhibitors. A potential limitation of the present study is the relatively small number of diabetic subjects in each of the three groups. However, given the reproducibility of cardiac MRI and its close agreement with the same parameters derived by echocardiography (76), as well as the reproducibility of the measurement of myocardial  $^{18}\text{F}$ -2-DOG uptake (19), we believe that the sample size (see below) will be sufficient to demonstrate significant effects of  $\beta$ -OH-B infusion on myocardial uptake of glucose, as well as on myocardial function. Lastly, we think that it is possible, although unlikely, that even the highest  $\beta$ -OH-B infusion rate (5.0 mmol/kg.min) may not have any effect on cardiac function even though myocardial  $\beta$ -OH-B uptake is increased and glucose uptake is reduced. If so, this would argue against a role for enhanced myocardial ketone uptake in the CV benefit of empagliflozin and canagliflozin in the EMPA-REG OUTCOME and CANVAS studies (5). Alternatively, it is possible that  $\beta$ -OH-B must be infused for longer than 6 hours to observe its beneficial effects on myocardial function. If the high  $\beta$ -OH-B infusion rate fails to increase parameters of LV function, we are prepared to admit diabetic patients to the CRC for a 72 hour  $\beta$ -OH-B infusion prior to performing the cardiac MRI.

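### Predicted rises in E/A ratio, diastolic volume and filling rate cannot be told apart from a preload effect, chiefly in Groups I and III

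*Combined protocol and SAP*

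**What the plan says.** The Study Protocol text under Experimental Design lists the MRI measures of "LV diastolic function (E/A ratio, peak LV filling rate, diastolic volume) and LV systolic function". Expected Results gives them a direction: "LV diastolic (E/A ratio, diastolic volume, peak LV filling rate), as well as systolic (cardiac index, EF, peak LV ejection rate), function will increase". It then anticipates that the higher β-OH-B levels "will elicit a significant improvement in multiple parameters of LV systolic and diastolic function", says this would support the ketone hypothesis, and makes a possible longer infusion depend on whether the high rate raises LV parameters.

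Data Analysis takes the rates from the "respective maximal and average downslope and upslope of volume time curves to determine peak LV ejection (PLVER) and filling (PLVFR) rates". The only scaling it states is to body surface area, and only for dimensional parameters. No division by EDV or stroke volume is mentioned.

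On control, the Study Protocol text and Table 2 give Group II a second full MRI day with NaHCO3 at the same infused volume. The same text says that no such study is planned for the low and high doses, though one may be added. Statistical Analysis specifies a two-sided paired t-test of baseline against post-β-OH-B and names no comparison with the NaHCO3 day. The protocol also says "Strain and tagging also will be measured", and NT-proBNP is drawn after the infusion, but no interpretive use is given for either.

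**The concern.** Diastolic function is part of the Specific Aim and of the hypothesis, and the plan reads a rise in three measures as better function. All three can also rise when the ventricle is filled from a higher pressure or with more volume. E/A is not monotone: it is low with impaired relaxation and high with restrictive filling, so the same rise can mean better or worse. A filling rate read from an unindexed volume-time curve grows with the chamber. These are points of general physiology, not statements in the documents.

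The documents supply the setting: reduced-EF, NYHA II-III patients, an intravenous infusion, and a stated wish to avoid volume overload. If infused volume also rises with dose, load can produce the graded response that Expected Results would credit to ketones. A before-after test without a control cannot separate the two.

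**Working it through.** The plan gives no figure for the diastolic measures; its sample size rests on EF. There is therefore no plan figure to reproduce. Three checks follow.

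**1. Does infused volume rise with dose?** Inputs from the Study Protocol text: 100 mg/mL; prime for 20 min, then a constant rate; 6 h in Groups I and II, 3 h in Group III. Body weight of 80 kg is my assumption.

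Volume (mL/kg) = (prime × 20 + rate × remaining minutes) / 100.

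| Group | mg/kg over the full infusion | mL/kg | mL at 80 kg | mL at 60 to 110 kg |
|---|---|---|---|---|
| I | 0.4 × 20 + 0.2 × 340 = 76 | 0.76 | 61 | 46 to 84 |
| II | 1.5 × 20 + 0.75 × 340 = 285 | 2.85 | 228 | 171 to 314 |
| III | 4.0 × 20 + 2.0 × 160 = 400 | 4.00 | 320 | 240 to 440 |

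The repeat MRI begins after 5 h (2 h in Group III), so the volume given by then is smaller:
- Group I: (8 + 0.2 × 280) × 80 / 100 = 51 mL
- Group II: (30 + 0.75 × 280) × 80 / 100 = 192 mL
- Group III: (80 + 2.0 × 100) × 80 / 100 = 224 mL

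The order by dose is the same either way. Over the full infusion, 300 mL is passed above 300 / 4.00 = 75 kg in Group III and above 300 / 2.85 = 105 kg in Group II. The 300 mL limit stands in the paragraph on the Group II control, and whether it also binds Group III is not clear.

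**2. Does the stated scaling remove a load change?** Body surface area is in effect constant within a patient on one day, so it cancels from a before-after ratio. As an illustration with assumed values, take EDV from 200 to 210 mL (+5%), with EF held at 45% and heart rate and curve shape unchanged.
- Stroke volume: 200 × 0.45 = 90 mL; 210 × 0.45 = 94.5 mL (+5%).
- Peak filling rate, peak ejection rate and cardiac index scale with EDV: +5% each.
- Either rate divided by EDV: 1.05 / 1.05 = 1, no change.

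Under these assumptions the proportional rise in the raw rates equals that in EDV, whatever its size. The zero change in the indexed rates follows from the fixed curve shape. It shows that indexing removes the chamber-size part, not that the index is free of load. E/A has no comparable calculation.

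**3. What would the planned test do with a pure load shift?** The size of any shift is not in the documents, so I take d = 0.25, 0.5 or 0.75 standard deviations of the paired difference. The chance of a significant rise is P(T > t(0.975, n−1)), where T is noncentral t with n−1 degrees of freedom and noncentrality d√n. Sample Size gives 23 evaluable per group; the Study Protocol text gives 19.

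| d | n = 19 | n = 23 |
|---|---|---|
| 0 | 0.025 | 0.025 |
| 0.25 | 0.18 | 0.21 |
| 0.5 | 0.54 | 0.63 |
| 0.75 | 0.87 | 0.93 |

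A moderate load effect would therefore often appear as a significant diastolic rise in a group without a control.

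**The case against.** The strongest reply is that the plan already has a volume control. The NaHCO3 day in Group II uses the same subjects, the same volume, and imaging before and after; a pure volume response would appear on both days. That stands, and a reader who inferred that volume is uncontrolled throughout would be wrong. What remains is that no analysis uses that day and that Groups I and III have no equivalent. The match is also on volume only: Table 2 gives 0.8 M for β-OH-B and 0.12 M for NaHCO3. If each mole of β-OH-B carries one mole of sodium (an assumption), 228 mL delivers 182 mmol against 27 mmol.

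A reader might also infer that the plan would score a fall in filling pressure as failure, or that its diastolic conclusion will have the wrong sign. The documents do not support this. Expected Results is a narrative with no scoring rule for each parameter, the test is two-sided, MRI reading is blinded, and a true improvement could also raise these measures. The defect is ambiguity, not reversal.

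Nor does the Background contradict the expected direction. It lists haemodynamic factors, "including the simultaneous reduction in preload (8) (secondary to mild intravascular volume depletion) and afterload", as one explanation of the SGLT2-inhibitor benefit and then offers the ketone hypothesis as an alternative. It predicts nothing about diastolic volume during an acute ketone infusion.

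Finally, EF, on which the sample size rests and the only outcome named for the three-group ANOVA, is less exposed: it does not move when stroke volume rises in proportion to EDV. It is not immune. With end-systolic volume (ESV) held at 110 mL instead, EDV of 210 mL gives EF = 100 / 210 = 47.6%. The point here is confined to the diastolic reading.

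**Conclusion.** The concern holds for the interpretation of the diastolic measures. As written, a rise in E/A, diastolic volume or unindexed filling rate cannot be attributed to better diastolic function rather than load. This applies chiefly in Groups I and III, and in Group II until the NaHCO3 day enters the analysis. Because infused volume rises about fivefold from Group I to Group III (320 / 61 = 5.2 at any common weight), a graded response alone would not settle the matter.

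This rests on general physiology and on the stated rates and concentration; the millilitre figures also rest on the assumed 80 kg. The size of any preload shift is unknown, and Group I receives little volume. Severity: should-fix. The remedy is cheap and needs no new data.

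**What to change.** 1. In Data Analysis and Expected Results, report peak filling and ejection rates divided by EDV alongside the raw rates.
2. Report EDV and ESV as loading measures. State that a rise in EDV or in E/A alone does not count as improvement, and read E/A as two-directional against each subject's baseline filling pattern.
3. In Statistical Analysis, add for the Group II diastolic measures a paired test of (post − baseline, β-OH-B day) − (post − baseline, NaHCO3 day). Limit diastolic claims in Groups I and III to what the EDV-indexed rates support.
4. Use strain/tagging and NT-proBNP as supportive context, not as a decision rule. Align the baseline NT-proBNP sample, which the Study Protocol text places on the MRI day but Tables 1 and 2 list only at screening and after infusion.
5. Reconcile the 300 mL limit with the Group II and III infusion rates.

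The cost is wording, a division of quantities already derived from the same images, and one further paired test. Data Analysis describes no strain processing, so its use would need describing. Fewer parameters can then count as benefit, and EDV-indexed rates are less load-dependent, not load-free. If the changes on the two days have equal SD σ and correlation ρ, the contrast in item 3 has variance 2(1 − ρ)σ². It is then less precise than the one-day change when ρ is below 0.5; the documents give no value for ρ.

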## Statistical Analysis

Data are expressed as mean  $\pm$  SD or as percentages. Statistical analyses will be performed using R 3.2.1 statistical software with RStudio IDE, Version 0.99.467. Paired, two-sided Student's t-test will be used to evaluate the null hypothesis of no difference between baseline and post  $\beta$ -OH-B butyrate protocol.  $p<0.05$  is deemed significant. Pearson's product-moment correlation will be used to examine the relationship between changes in parameters of LV diastolic and systolic function and coronary blood versus changes in myocardial  $\beta$ -OH-B uptake and both univariate and multivariate ANOVA for changes in EF in the 3 different  $\beta$ -OH-B infusion groups.

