
## SAMPLE SIZE

Studies in the literature have demonstrated that an increase in 6-minute walk distance of 37 meters is of clinical significance and can be observed with a 10% increase in left ventricular ejection fraction (EF) in patients with Class II-III NYHA (87). In the present study we expect that the baseline EF will be  $45\pm2\%$ . To observe at least a 10% increase in EF with an autocorrelation of 0.96 and an alpha = 0.05 and 90% power following  $\beta$ -OH-B infusion would require 23 subjects per group. With a 10% drop out rate, one needs to recruit 26 subjects per group ([name], Professor, Dept. of Biostatistics and Epidemiology, UTHSCSA).

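### The plan promises to define the effective ketone level but has no method for it; differing within-group significance should not be read as a threshold

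*Combined protocol and SAP*

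**What the plan says.** Expected Results predicts that the physiologic (+0.5 mmol/L) and pharmacologic (+2.0 and +5.0 mmol/L) "levels will cause a dose-response increase in parameters of LV diastolic/systolic function". It then says the results will let the authors define the concentration at which "beneficial effects on CV function are observed". It expects significant improvement at 2.0-5.0 mmol/L. It adds that benefit at the low dose would allow generalisation to most patients on SGLT2 inhibitors.

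Statistical Analysis provides this: "Paired, two-sided Student's t-test will be used to evaluate the null hypothesis of no difference between baseline and post" β-OH-B infusion, at p<0.05. It also lists univariate and multivariate ANOVA of EF change across the three infusion groups. It gives no pairwise contrasts, dose-response model, confidence-interval criterion or rule for naming an effective level.

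SAMPLE SIZE uses one target for every group. The aim is "To observe at least a 10% increase in EF with an autocorrelation of 0.96 and an alpha = 0.05 and 90% power", which "would require 23 subjects per group", or 26 with 10% dropout. Baseline EF is expected to be 45 ± 2%. No expected effect is given for any single dose. The Study Protocol section still prints 19 subjects per group.

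**The concern.** The promise to define a concentration compares levels, yet the only test of benefit at a given level looks at one group at a time. A result of significant in Groups II and III but not in Group I invites the conclusion that benefit starts somewhere between +0.5 and +2.0 mmol/L. A difference in significance is not a test that the levels differ.

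The stakes are highest for Group I. The Study Protocol section describes an increment of about 0.5 mmol/L as the one usually seen on an SGLT2 inhibitor, and increments of 2-5 mmol/L as seen in roughly 5-10% of patients. If a non-significant Group I were read as no effect, the ketone hypothesis would be confined to that minority, possibly only because the group was too small for a smaller effect.

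**Working it through.** **Inputs.** From SAMPLE SIZE: baseline EF 45, SD 2, correlation 0.96, alpha 0.05, power 90%, n = 23 per group. From Statistical Analysis: two-sided paired t-test. A 10% rise is read as relative: 0.10 × 45 = 4.5 EF points.

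**Step 1: the plan's own figure.** SD of change = 2 × √(2 × (1 − 0.96)) = 0.566 points. The standardised effect is 4.5/0.566 = 7.95, and 90% power needs n = 3, not 23. Variants tried for a 4.5- or 10-point rise (one-sided, alpha 0.05/3, correlation 0, SD of change 2, ±2 taken as a standard error) give 1 to 7. Only the dropout step reproduces: 23/0.9 = 25.6, so 26.

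Backing out instead: n = 23 gives 90% power at a standardised effect of 0.7075.
- On the printed SD and correlation, that is 0.7075 × 0.566 = 0.40 points.
- For 4.5 points it requires an SD of change of 4.5/0.7075 = 6.36.

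**Step 2: identical true effects.** Let each group have power p. The three independent groups disagree (at least one significant, at least one not) with probability 1 − p³ − (1 − p)³.
- Claimed power, p = 0.90: 1 − 0.729 − 0.001 = 0.27.
- Half the target effect, p = 0.368: 1 − 0.050 − 0.252 = 0.70.

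This needs no dose shape. It needs only that 90% be the true power for the effect present.

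**Step 3: effects that rise with dose.** The plan gives no effect by dose, so the shape is an assumption. Power comes from the noncentral t with noncentrality effect × √23 / SD of change.

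| Assumed linear response | SD of change | Effect at +0.5 / +2.0 / +5.0 (points) | Power I / II / III |
|---|---|---|---|
| 10% reached at +5.0 | 6.36 | 0.45 / 1.8 / 4.5 | 6% / 25% / 90% |
| 10% reached at +2.0 | 6.36 | 1.125 / 4.5 / 11.25 | 13% / 90% / ~100% |
| 10% reached at +5.0 | 2 | 0.45 / 1.8 / 4.5 | 18% / 98% / ~100% |
| 10% reached at +5.0 | 0.566 (printed inputs) | 0.45 / 1.8 / 4.5 | 95% / ~100% / ~100% |

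If 10% were already reached at +0.5, every group would have at least 90% power even at SD 6.36.

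**Step 4: what a direct contrast can show.** At SD 6.36 the standard error of a difference between two groups of 23 is 6.36 × √(2/23) = 1.88, so the 95% half-width is about 2.015 × 1.88 = 3.8 points. In the first row of the table the I versus III interval would exclude zero in about 56% of trials, although Group I truly improves. Such an interval shows a smaller effect at the lower level, not absence of effect.

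**The case against.** The strongest reply is that the plan never says the level will be defined by which groups reach p<0.05. That is true. The promise sits in narrative text, and the ANOVA of EF change is a direct between-group analysis. What remains is that the ANOVA asks whether the groups differ somewhere. It names no contrasts and does not identify a level, so the paired tests are the only listed evidence of benefit at a given concentration.

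A reader might also infer that 90% power cannot hold in all three groups if effects grow with dose. The documents do not support this. SAMPLE SIZE speaks of at least a 10% rise, justified by clinical relevance, and sizing every arm on one minimum important difference is ordinary practice. A rising response could reach 10% at +0.5 and exceed it above.

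The figures of 6%, 25% and 90% should not be quoted as the plan's operating characteristics. They need 10% to be reached only at +5.0 and a back-solved SD about eleven times the one implied by the printed inputs. The Study Protocol section expects about 2 mmol/L to be adequate for improvement, which suits the +2.0 anchor at least as well. On the printed inputs, power at +0.5 is 95% and the power concern largely goes. But those inputs contradict n = 23, so they cannot be used to dismiss it.

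Finally, the plan does not say that a non-significant Group I would mean no effect. Its statement about the low dose is a positive conditional, and it admits that the groups are small. The misreading is invited, not written.

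**Conclusion.** The point holds in a limited form. The plan claims it will define an effective concentration, but it specifies no contrast, interval or model that could do so. The natural substitute, comparing significance across groups, is not evidence that levels differ. Groups with identical true effects disagree in 27% of trials at the claimed operating point and in 70% at half the effect.

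How often Group I would be missed for lack of power cannot be settled from the documents. Under the linear shapes tabulated it ranges from nearly always (power 6% or 13% at SD of change 6.36) to rarely (power 95% at 0.57). It depends on the dose shape, which is not stated, and on the SD of change, where the printed inputs and n = 23 conflict and must be reconciled. The documents do not support saying that the plan adopts a p<0.05 threshold rule, or that a threshold found would merely mark where power runs out.

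**What to change.** **Statistical Analysis and Expected Results.** Report the mean EF change with a 95% CI for each level, and the differences in EF change for I vs II, I vs III and II vs III with 95% CIs. State that non-significance in a group will not be read as absence of effect, and that no threshold concentration will be claimed from differing within-group significance. State also that a between-group interval excluding zero shows a smaller effect at the lower level, not that this level is ineffective.

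Add that these contrasts do not isolate concentration: Group III is infused for 3 hours and the others for 6, and the NaHCO3 control is planned only in Group II.

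**SAMPLE SIZE.** Reconcile the SD, correlation and n. Then give the EF change detectable with 90% power from the reconciled SD of change: 0.71 × SD at 23 per group, and 0.79 × SD at the 19 per group printed in Study Protocol. For scale, that is 0.40 and 0.45 points at SD 0.57, or 4.5 and 5.0 points at SD 6.36.

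**Cost.** A few extra reported estimates, with no added subjects or procedures, and a less definite claim about the effective level. If the SD of change is near 6.36, the contrasts will be wide.

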glucose, FFA, lactate, pyruvate, glycerol, HCO3, insulin, glucagon, renin and aldosterone. Axial and sagittal localizer views, standard two-, three-, and four-chamber views, with 7 mm thick slices are obtained using gradient echo sequence (2.2 x 1.3 mm^2 pixel). Cine imaging with retrospective gaiting is used with a balanced steady-state free precision sequence (TR/TE = 2.44/1.22 ms). Acquisitions consist of 25-30 cardiac phases, matrix 224 x 288, FOV 336 x 430 mm^2, 1.5 x 1.5 mm^2 pixel area. Contiguous short-axis slices are acquired during repetitive breath-holds at expiration. Mitral inflow images are obtained using phase-contrast gradient-echo (PCGE) sequence with through-plane velocity encoding (Venc = 100 cm/s) at the mitral valve with flip angle = 10° and TR/TE = 5.8/3.6 ms. PCGE slice thickness was 8 mm with typical FOV = 228 x 430 mm^2, matrix = 192 x 102, producing 2.89 x 2.89 x 8.0 mm pixel volumes.

Following completion of the baseline MRI, subjects will be divided into three groups (19 subjects per group). Each group will receive a 6-hour (3-hour in group III) prime-continuous infusion of racemic  $\beta$ -OH-B (100 mg/mL solution; pH adjusted to 7.4) to increase the plasma  $\beta$ -OH-B concentration by ~0.5, ~2.0, and ~5.0 mmol/L (43,74).

GROUP I: Prime = 0.4 mg/kg.min for 20 minutes and constant rate = 0.2 mg/kg.min until study end

GROUP II: Prime = 1.5 mg/kg.min for 20 minutes and constant rate = 0.75 mg/kg.min until study end

GROUP III: Prime = 4.0 mg/kg.min for 20 minutes and constant rate = 2.0 mg/kg.min until study end

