Currently, it is not known what plasma  $\beta$ -OH-B level is required to observe an improvement in LV diastolic/systolic function. Based upon the study of Gormesen et al (70), we anticipate that an increase in plasma  $\beta$ -OH-B of ~2 mmol/L will be adequate to augment myocardial  $\beta$ -OH-B uptake sufficiently to switch the myocardium from glucose to ketone utilization and result in an improvement in cardiac function. Therefore, subjects in GROUP II will be studied on two occasions with NaHCO3 infusion to serve as time controls. Since we previously have shown that Na- The total volume of  $\beta$ -OH-B and NaHCO3 to be infused will be the same to obviate any effect of volume on cardiac function. Blood glucose and electrolytes will be monitored similarly as described above for  $\beta$ -OH-B infusion. As mentioned above, the volume will not exceed 300 ml to avoid volume overload. We are unaware of any evidence that the NaHCO3 infusion has any effect on cardiac function. We have not included a time control study for the low and high dose B-OH-B infusion studies although, depending

upon the results with the lower and higher B-OH-B infusions, we may choose to perform the control NaHCO3 infusion in these groups as well.

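### A 72-hour infusion held in reserve only for a null at the highest rate gives the hypothesis a second, unplanned and uncontrolled test, and the 300 mL volume limit does not fit the stated rates

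*Combined protocol and SAP*

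**What the plan says.** Expected Results considers the case in which even the highest rate leaves cardiac function unchanged and says "this would argue against a role for enhanced myocardial ketone uptake". It then offers an alternative, that β-OH-B "must be infused for longer than 6 hours to observe its beneficial effects on myocardial function". The paragraph closes with the contingency: if the high rate does not improve LV function, "we are prepared to admit diabetic patients to the CRC for a 72 hour" infusion, followed by the cardiac MRI.

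The planned infusions are in the Study Protocol text. Groups I and II are infused for 6 hours and Group III for 3 hours, with a solution described as "100 mg/mL solution; pH adjusted to 7.4". The lowest rate is "GROUP I: Prime = 0.4 mg/kg.min for 20 minutes and constant rate = 0.2 mg/kg.min until study end". The highest is "GROUP III: Prime = 4.0 mg/kg.min for 20 minutes and constant rate = 2.0 mg/kg.min until study end". Group II receives a prime of 1.5 mg/kg.min for 20 minutes and then 0.75 mg/kg.min.

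The paragraph on the NaHCO3 time control says the volumes of β-OH-B and NaHCO3 "to be infused will be the same to obviate any effect of volume on cardiac function", and that "the volume will not exceed 300 ml to avoid volume overload". The time control is planned for Group II only. One may be added for the low and high groups, depending on their results. No control is mentioned for a 72-hour infusion.

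**The concern.** The reserve option opens only when the result is unfavourable. A positive result at the high rate ends the enquiry, while a negative one allows another attempt under different conditions. No sentence says which of the two attempts carries the trial's conclusion. The trigger is loose as well: it refers to LV function parameters in general, with no named parameter or threshold. Group III, which pulls the trigger, is infused for only 3 hours, so an explanation that more than 6 hours may be needed is open to it from the start.

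The second attempt would also be harder to interpret. A before-after comparison across an admission of about three days, without a time control, cannot separate the effect of ketones from other change over those days.

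Volume is a further problem. The participants have NYHA Class II-III heart failure with reduced ejection fraction, and the protocol sets a volume limit expressly to avoid overload. A much longer infusion at anything like the stated rates would not fit that limit. On checking, some of the scheduled infusions do not fit it either.

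**Working it through.** **1. Is the 72-hour infusion planned anywhere else?**
- Tables 1 and 2: only the 6-hour and 3-hour infusions appear.
- Statistical Analysis: a paired two-sided t-test of baseline against post-infusion at p<0.05, correlations, and ANOVA across the three groups. There is nothing for a 72-hour infusion and no adjustment for a second test.
- Sample Size: one calculation per group for the planned study.
- Not stated for the 72-hour option: rate, number of patients, whether they are new or already studied, control, alpha, analysis.

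**2. Error rate with a second test.** Take one parameter, no true effect and two unadjusted two-sided 0.05 tests.
- False finding in either direction, independent tests: 1 − 0.95² = 0.0975. By simulation this falls to about 0.091 at correlation 0.5 and 0.078 at 0.8.
- False finding of improvement only: one test gives 0.025. Two independent tests give 1 − 0.975² = 0.0494. By simulation this is about 0.045 at correlation 0.5 and 0.039 at 0.8.

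Both maxima assume the tests are independent or positively correlated.

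**3. The 300 mL limit against the scheduled infusions.** The limit is stated, not derived, so there is no figure to reproduce. It can be compared with the planned durations first.

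mL/kg = [prime × 20 + rate × (minutes − 20)] / 100 mg/mL; weight at which 300 mL is reached = 300 / (mL/kg).

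| Infusion | mg/kg | mL/kg | Exceeds 300 mL above |
|---|---|---|---|
| Group I, 6 h | 0.4×20 + 0.2×340 = 76 | 0.76 | 395 kg |
| Group II, 6 h | 1.5×20 + 0.75×340 = 285 | 2.85 | about 105 kg |
| Group II PET day, 380 min | 1.5×20 + 0.75×360 = 300 | 3.00 | 100 kg |
| Group III, 3 h | 4.0×20 + 2.0×160 = 400 | 4.00 | 75 kg |

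An 80 kg participant in Group III would receive 320 mL on schedule.

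**4. The same formula at 72 hours (4,320 min), assuming the stated rates and concentration carry over.** The documents give a BMI range but no weights, so 70 kg and a range of 50-120 kg are assumed.

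| Rate | mg/kg | mL/kg | At 70 kg | At 50-120 kg |
|---|---|---|---|---|
| Group I | 0.4×20 + 0.2×4,300 = 868 | 8.68 | 608 mL | 434-1,042 mL |
| Group II | 1.5×20 + 0.75×4,300 = 3,255 | 32.55 | 2,278 mL | 1,627-3,906 mL |
| Group III | 4.0×20 + 2.0×4,300 = 8,680 | 86.8 | 6,076 mL | 4,340-10,416 mL |

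At the Group I rate, 300 mL is reached at 300/8.68 = 34.6 kg. At the minimum eligible BMI of 23 that weight means a height of √(34.6/23) ≈ 1.23 m, so on these assumptions essentially every eligible adult would exceed the limit. At 70 kg the Group III rate gives 6,076/300 ≈ 20 times the limit.

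**5. Sensitivity.**
- If 300 mL were a daily limit, the first 24 hours at the Group I rate, with prime, would be (8 + 0.2×1,420)/100 = 2.92 mL/kg, within the limit up to about 103 kg. The Group II and III constant rates give 10.8 and 28.8 mL/kg per day and would exceed it above about 28 kg and 10 kg.
- Tables 1 and 2 give the solution as 0.8 M. If that means about 83 mg/mL (an assumption: free acid), all volumes are about 20% larger.
- Expected Results gives the highest rate as 5.0 mmol/kg.min, which does not agree with 2.0 mg/kg.min in the Study Protocol text.

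**The case against.** The best defence is that the 72-hour infusion is not part of the scheduled study. It is a closing remark in Expected Results, and its absence from the tables and the analysis fits a possible later project. Much of this stands, and it is why the remedy is mainly one of wording. It does not remove the problem, because nothing in the text places the option outside this trial, and its trigger is this trial's null.

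Three stronger readings are tempting, and the documents do not support them.

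- A reader might infer that a null could never count as a null. The text contradicts this: it says such a result would count against the hypothesis, and offers short duration only as an alternative. The plan leaves open which reading prevails.
- A reader might infer that the contingency definitely breaks the volume limit at every stated rate. No rate, concentration or volume is given for the 72 hours. The limit stands in the paragraph on the planned infusions, refers back to an earlier mention that the available text does not show, and follows a broken-off sentence, so its scope is unclear. It is not said to cover a multi-day infusion. On a per-day reading, which the text does not state, the Group I rate would pass for most weights.
- A reader might take 9.75% as the trial's false-positive rate. It is a two-directional figure under independence. Only improvement supports the hypothesis, so the relevant ceiling is 4.9%. The plan already tests several LV parameters in three groups without adjustment, so this is a small part of its multiplicity.

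**Conclusion.** The concern holds in a limited form. As written, a null at the highest rate is not final: it opens a second test with no stated rate, control, sample size or analysis. For a single parameter, the chance of falsely finding improvement rises from 2.5% to at most 4.9%. The missing control matters at least as much as that increase, because a positive 72-hour result could not be attributed to ketones.

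The volume finding has two parts of different strength. The firmer one concerns the scheduled study: at the stated rates and 100 mg/mL, the 300 mL limit is passed above 75 kg in Group III and above about 105 kg in the 6-hour Group II infusion. The weaker one concerns the 72-hour option: 8.68, 32.55 and 86.8 mL/kg follow only if the stated rates and concentration carry over, and they breach the limit only if it applies to a multi-day infusion.

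**What to change.** In Expected Results, state that the trial's conclusion rests on the planned infusions whatever their result. State also that any 72-hour infusion would be a separate, exploratory study under its own protocol, with its own control, sample size and analysis.

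Separately, the clinical team must reconcile the infusion rates and durations, the 300 mL limit and its scope, the solution strength, and the highest rate quoted in Expected Results. These stand in the Study Protocol text, Tables 1 and 2 and Expected Results. No rate, duration or limit is proposed here.

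The statistical change costs one or two sentences. The downside is that the contingency leaves this protocol and would need its own approval if the investigators wish to pursue it.
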